#### **4.6 Data Management and Security**

For the purposes of this study, each subject will be assigned a unique randomly generated ID number, which will be used on all electronic data stored locally. A walk across file will be maintained to link the subject with the random ID number and will be encrypted and stored in a separate location from all other data extracted. Only the study coordinator and PI will have access permissions to this file.

All electronic databases related to this protocol will be stored locally on a VA server in an entry controlled, locked room at the Jamaica Plain campus of the VA Boston Healthcare System. There are multiple levels of security to ensure the integrity and confidentiality of all data. The computer system operates entirely within the

VA network, which is protected by a firewall maintained by the VA Office of Information Technology. Only authorized users can log on to the server. An additional layer of restrictions is at the file and directory level. Users can only access portions of the data to which they are entitled. Access to all data on the server is password protected. Access permissions will be removed and passwords will be changed whenever study personnel are no longer part of the research team. All paper forms will be secured in a locked fireproof study cabinet. Only the PI will have keys to the study cabinet. All data will be kept indefinitely or until the law allows their destruction in accordance with the VA Record Control Schedule. Records will be destroyed, when allowed, in the following manner: paper records will be shredded and electronic records will be destroyed in a manner in which they cannot be retrieved. All suspected or identified information security incidents (e.g. theft or loss of data, theft or loss of smartphones, unauthorized access) will be reported to the PI, ISO, and PO immediately upon suspicion by study staff.

To minimize data entry errors, all data collected on paper forms will be entered twice by a trained staff member using software that allows specification of valid responses for each entry field. Upon second entry of each record, the software will analyze each field to check for discrepancies in the two entries. Entry errors will be corrected on the spot and any errors requiring more extensive review will be deleted and re-keyed after the errors are resolved. In addition, the data manager will perform a careful quality assessment of all measures through logic and consistency checks and distributional assessment of overall distributions of responses. Data at follow-up exams will be compared to previous data for longitudinal consistency. Any patterns in missing or erroneous data will be discussed with the staff members collecting the data to determine the cause of the problem and what corrective measures will be taken. Databases will be carefully versioned so that all analyses can be clearly audited.

#### **4.7 Data Analyses**

The intervention and control groups will be compared on the ADAS-Cog scale with the use of PROC MIXED (SAS) to estimate regression parameters based on a mixed-effects longitudinal model (Diggle et al., 1994). Initially, the regression parameter representing the differential change in ADAS-Cog for TLC-WALK vs. control between 6 months and baseline will be assessed. In addition, we will compare the intervention and control groups at 12 months and 18 months of follow-up using the appropriate regression parameters from the model.

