##### **4.3.1 Randomization**

All subjects are recruited with the understanding that they will be randomized to one of two groups: one group will be assigned to use the TLC-WALK system (see Section 4.4.1) and the other group will use the health education control TLC system (see Section 4.4.2). A staff member will be in charge of the randomization and all the tasks related to group assignment. At the conclusion of the baseline visit, half of the 160 subjects will be randomized to each experimental arm with a computer-based algorithm for group assignment, which cannot be modified once the inclusion parameters are specified for a given subject.

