#### **4.5 Outcome Data Collection**

We will assess the ADAS-Cog (Rosen et al., 1984) at baseline, 6 months, 12 months, and 18 months at the Jamaica Plain campus of the VA Boston Healthcare System. This will be collected by a trained staff member who will be blinded to group assignment. The ADAS-Cog also was assessed as part of the physical activity intervention study of Lautenschlager et al. (2008). The scale consists of eleven items assessing memory, orientation, language, and praxis, with scores ranging from 0 (least impaired) to 70 (most impaired).

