#### **4.8 Power Considerations**

In Lautenschlager et al. (2008), among subjects with MCI, the walking group improved more than the control group in ADAS-Cog at 6 months (Table 2) with a mean difference of 2.16 between groups. This results in an effect size of 0.580 standard deviations between groups. A total of 128 participants (64 per group) will be required to provide 90% power to detect as significant, at the 5% level, an effect size of 0.580 for TLC-WALK subjects compared with control subjects.

Table 2

ADAS-Cog score	Exercise Group (n=48)	Control Group (n=52)
6 months	-0.87 (-1.83 to 0.08)	1.29 (0.20 to 2.39)

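### Section 4.7 does not say how baseline ADAS-Cog enters the model; with a free baseline mean in each arm, the 6-month contrast may give up a variance saving of about nil to one third (assumed inputs)

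*Combined protocol and SAP*

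**What the plan says.** Section 4.7 (Data Analyses) is the whole analysis plan. It uses PROC MIXED "to estimate regression parameters based on a mixed-effects longitudinal model". For the first comparison, "the regression parameter representing the differential change in ADAS-Cog for TLC-WALK vs. control between 6 months and baseline will be assessed". For the later visits, "we will compare the intervention and control groups at 12 months and 18 months of follow-up using the appropriate regression parameters from the model". It lists no fixed effects, covariates, covariance structure or constraint on the baseline means, and no other section supplies them.

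Section 4.5 has ADAS-Cog measured "at baseline, 6 months, 12 months, and 18 months". Section 4.3.1 sets the order of events: "At the conclusion of the baseline visit, half of the 160 subjects will be randomized to each experimental arm". The baseline score is therefore available before allocation.

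Section 4.8 sizes the trial from the 6-month changes in its Table 2: "This results in an effect size of 0.580 standard deviations between groups", and "A total of 128 participants (64 per group) will be required to provide 90% power".

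**The concern.** Defining the parameter as a between-arm difference in change implies that baseline is one of the repeated responses. It does not settle whether the two arms have separate baseline means or share one.

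- **Separate means.** With group, visit and group-by-visit terms and complete data, the 6-month interaction term is the difference between arms in mean change score. Baseline is subtracted with a fixed weight of one, whatever its correlation with the 6-month score.
- **Common mean, or baseline as a covariate.** The data set the weight on baseline, and the contrast has the smaller, baseline-adjusted variance.

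Randomization makes both forms valid, but they give different standard errors and p-values from the same data. At stake is precision on the main comparison that data already being collected could supply, and an analysis choice that should be fixed in advance. Neither bias nor the adequacy of the sample size is in question.

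**Working it through.** **The plan's own figures.** Inputs are from Section 4.8 and its Table 2, with the intervals read as simple 95% intervals.

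- Exercise arm: SD = [(0.08 + 1.83)/2]/1.96 × √48 = 3.38.
- Control arm: SD = [(2.39 − 0.20)/2]/1.96 × √52 = 4.03.
- Pooled SD = √[(47 × 3.38² + 51 × 4.03²)/98] = 3.73, and 2.16/3.73 = 0.579, against 0.580 stated.
- Two-sided 5% t-test at 0.580: power 0.898 at 63 per arm and 0.902 at 64. The stated 64 per arm is reproduced. At 80 per arm (all 160 subjects) power is 0.954.

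The effect size is thus in SDs of whatever Table 2 reports. The values are changes; the table does not say whether they are adjusted for baseline.

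**Variance of the 6-month contrast.** Let s0 be the baseline SD, k the 6-month SD divided by the baseline SD, and r the correlation between the two scores. The documents give neither k nor r, so both are assumptions. Per subject, with complete data and the same covariance in both arms:

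- separate baseline means (change score): s0²(1 + k² − 2rk)
- common baseline mean or covariate: s0²k²(1 − r²)
- gross saving S = (1 − rk)²/(1 + k² − 2rk), which is (1 − r)/2 at k = 1 and zero at rk = 1

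Estimating the baseline weight inflates the expected variance by 1 + 1/(2n − 4): 1/124 = 0.8% at n = 64 per arm and 1/156 = 0.6% at n = 80. Net saving = 1 − (1 − S)(1 + 1/(2n − 4)).

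Two worked cells at n = 64:

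- k = 1, r = 0.5: S = 0.5²/1 = 25.0%; net = 1 − 0.750 × 1.0081 = 24.4%.
- k = 0.9, r = 0.5: S = 0.55²/0.91 = 33.2%; net = 32.7%.

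**Net saving at 64 per arm (gross in brackets)**

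| k | r = 0.5 | r = 0.7 | r = 0.8 |
|---|---|---|---|
| 0.9 | 32.7% (33.2%) | 24.3% (24.9%) | 20.6% (21.2%) |
| 1.0 | 24.4% (25.0%) | 14.3% (15.0%) | 9.3% (10.0%) |
| 1.2 | 12.2% (12.9%) | 2.6% (3.4%) | −0.5% (0.3%) |
| 1.25 | 10.0% (10.7%) | 1.1% (1.9%) | −0.8% (0.0%) |

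Over a fine grid of r 0.5 to 0.8 and k 0.9 to 1.25 the gross saving runs from 0.0% to 33.2%. Neither r nor k is bounded by that window: k = 1 with r = 0.9 gives 4.2% net, and k = 0.8 gives 35% to 42% net for r of 0.5 to 0.8. The direction of k matters: with the ratio inverted, the same numbers would give 3% to 43% gross.

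Simulation of 20,000 trials at 64 per arm gave savings of 32.5% (r = 0.5, k = 0.9), 16.9% (r = 0.65, k = 1; formula 17.5% gross) and −0.7% (r = 0.8, k = 1.25), in line with the net theory.

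**Power for 0.580**, if it is in SDs of unadjusted change (noncentral t, effect 0.58/√(1 − net saving), df 2n − 3):

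| | r = 0.5 | r = 0.7 | r = 0.8 |
|---|---|---|---|
| 64 per arm, unadjusted | 0.902 | 0.902 | 0.902 |
| 64 per arm, k = 0.9 | 0.978 | 0.963 | 0.955 |
| 64 per arm, k = 1 | 0.963 | 0.940 | 0.928 |
| 64 per arm, k = 1.25 | 0.929 | 0.906 | 0.900 |
| 80 per arm, unadjusted | 0.954 | 0.954 | 0.954 |
| 80 per arm, k = 0.9 | 0.994 | 0.987 | 0.984 |
| 80 per arm, k = 1 | 0.987 | 0.976 | 0.969 |
| 80 per arm, k = 1.25 | 0.970 | 0.956 | 0.953 |

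**The case against.** The strongest reply is that no loss has been shown. Section 4.7 lists no fixed effects at all, so it also admits a common baseline mean, in which case the gain is already taken. This stands, and the conclusion is conditional on it.

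The size rests wholly on assumed inputs, and 33% is one corner of the window. That corner needs the spread of ADAS-Cog to shrink by 10% over 6 months in patients whom Section 1 describes as likely to decline, and nothing in the documents supports that. On an even grid over the window the median net saving at 64 per arm is about 12%, and about 7% of the grid exceeds 25%; with k at or above 1 the median is about 9%. An even grid is only a summary device, but k = 1 is a fairer reference than the corner.

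The practical consequence may be small. Unadjusted power is already 0.902 at 64 per arm and 0.954 if all 160 subjects give 6-month data. If the Table 2 changes are already adjusted, the power comparison does not hold, although the variance formula does. Missing data would alter the figures, and the 12- and 18-month contrasts are not quantified.

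These points limit the size and certainty of the gain. They do not remove the case for stating the model: the expected cost of adjustment is under 1% of variance, and the two readings give different primary results.

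**Conclusion.** The point holds as an efficiency and specification improvement that should be made. If each arm keeps its own baseline mean, the primary 6-month contrast does not use baseline to reduce variance. Against that model, adjustment would lower the variance of the contrast by an unknown amount: about nil to 33% for r of 0.5 to 0.8 and k of 0.9 to 1.25, and 9% to 24% net at k = 1 with 64 per arm. The gain vanishes where r times k is near 1, and the most that adjustment is expected to cost is 0.8% of variance at 64 per arm. The figures assume complete data and equal covariance in the two arms. If the trial fits a common baseline mean, only the missing specification remains.

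**What to change.** In Section 4.7, specify PROC MIXED with visit as a categorical factor and an unstructured covariance across visits, and state one of two forms:

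1. All four visits as responses, with one baseline mean common to both arms (no group main effect) and group-by-visit terms at 6, 12 and 18 months; or
2. The 6-, 12- and 18-month values as responses, with group, visit, group-by-visit, baseline ADAS-Cog and baseline-by-visit terms.

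Name the 6-month group contrast from that model as the primary test, and the 12- and 18-month contrasts as the later comparisons. The unstructured covariance matters here: a random-intercept model with constant residual variance would impose equal SDs at every visit (k = 1) and so fix the weight given to baseline, instead of letting the data set it.

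The cost is one sentence and one MODEL statement, with an expected 0.8% of variance at 64 per arm (0.6% at 80). It needs no new data or visits, and the sample size does not change.

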#### **4.8 Power Considerations**

In Lautenschlager et al. (2008), among subjects with MCI, the walking group improved more than the control group in ADAS-Cog at 6 months (Table 2) with a mean difference of 2.16 between groups. This results in an effect size of 0.580 standard deviations between groups. A total of 128 participants (64 per group) will be required to provide 90% power to detect as significant, at the 5% level, an effect size of 0.580 for TLC-WALK subjects compared with control subjects.

Table 2

ADAS-Cog score	Exercise Group (n=48)	Control Group (n=52)
6 months	-0.87 (-1.83 to 0.08)	1.29 (0.20 to 2.39)

